6.0 CLINICAL FOLLOW-UP SCHEDULE

All subjects will be scheduled to return for follow-up examinations at defined intervals through 24 months. **Table 5** shows the schedule of events and procedures at each protocol-required visit.

TABLE 5: SCHEDULE OF EVENTS AND PROCEDURES

Procedure	Screening (Both Eyes) (w/in 30d of washout start)	Baseline (w/in 13d of minimum washout)	Surgery (w/in 14d of minimum washout)	1D Postop	7D Postop (±2d)	1M Postop (±7d)	3M Postop (±14d)	6M Postop (±21d)	12M Postop (-28d/ +42d)	18M Postop (±28d)	24M Postop (-28d/ +42d)	3Y, 4Y & 5Y Postop (±84d)
Ophthalmic and medical history	Х											
Ocular Medication Status	Х	Х	Х	Х	Х	Х	Х	Х	Х	Х	Х	X ⁵
Glaucoma Medication Status	Х	Х	Х	Х	Х	Х	Х	Х	Х	Х	Х	Χ5
Manifest Refraction	Х	Х			Х	Х	Х	Х	Х	Х	Х	
BCVA	X (Snellen)	X (ETDRS)		X (pinhol e) (Snellen	X (ETDRS)	X (ETDRS)	X (ETDRS)	X (ETDRS)	X (ETDRS)	X (ETDRS)	X (ETDRS)	X (Snellen)
IOP (Goldmann Applanation Tonometry)	Х			х	Х	Х	Х	Х	X ²	Х	χ2	X ₆
Washed Out Diurnal IOP (Goldmann Applanation Tonometry)		X1							X1		X1	
Pachymetry CCT	х							Х	Х		Х	Х
Gonioscopy	Х				Х	Х	Х	Х	Х	Х	Х	Х
Slit Lamp Exam	Х	Х		Х	Х	Х	Х	Х	Х	Х	Х	Х
Visual Field (Humphrey 24-2 SITA-Std)	Х							Х	Х		Х	Х
Fundus Exam/Disc evaluation	х					Х		Х	Х		Х	Х
Specular Microscopy	Х						Х	X ⁷	Χ7	X ⁷	χ7	Х7
Nerve Fiber Layer Imaging	χ³											
Ocular Symptom Questionnaire		Х							Х		Х	
Adverse Event Assessment		Χ4	Х	Х	Х	Х	Х	Х	Х	Х	Х	Χ8

^{*}Washed out diurnal IOP measurements will be performed after subject has washed out of any ocular hypotensive medications. All diurnal IOP measurement must be done PRIOR to the Gonioscopy, Fundus Exam and contact Pachymetry. An additional visit may be necessary to perform the diurnal IOP measurements.

*Only required for those subjects taking ocular hypotensive medications at the time of this visit.

*Only required for those subjects whose VF testing was not confirmatory for glaucomatous defect per the protocol defined criteria.

*Only adverse events associated with the ocular medication wash out.

*Study eye only for ocular medications other than hypotensive medications.

*Single operator tonometry may be conducted at 3, 4 and 5 year visits.

*Includes specular microscopy of the fellow eye for the central region only

*Report all SAEs and only study eye ocular AEs.

7.0 STATISTICAL ANALYSIS PLAN - STUDY ENDPOINTS

A. THE PRIMARY EFFECTIVENESS ENDPOINT FOR THIS STUDY

Percentage of subjects with a reduction of at least 20% (i.e., \geq 20%) in mean diurnal IOP from baseline in the study eye at 24 months following medication washout. These subjects were defined as "IOP responders."

Subjects were defined as non-responders if they did not achieve the primary effectiveness endpoint, they were missing 24-month IOP assessment outcomes, if ocular hypotensive medications were not washed out at the 24-month visit, if they underwent an IOP-affecting secondary surgical procedure (i.e., iridotomy, iridectomy, trabeculectomy, glaucoma shunt implantation, argon laser trabeculoplasty, selective laser trabeculoplasty), or other surgery that would affect IOP.

B. THE SECONDARY EFFECTIVENESS ENDPOINT FOR THE STUDY

The mean diurnal unmedicated IOP change from baseline at 24 months was compared between the Hydrus group and control group.

Each endpoint requires a comparison between the Hydrus and control groups. The primary effectiveness analysis will be performed using the Intent to Treat (ITT) population, consisting of all randomized subjects grouped according to their randomization assignment.

With regard to safety, anticipated and unanticipated AEs will be reported for all subjects randomized in the study. Best corrected visual acuity (BCVA), central corneal pachymetry, slit lamp and fundus exams, gonioscopy and central corneal endothelial cell density (ECD) will also be used to assess safety.

C. ACCOUNTABILITY OF PMA COHORT

Subjects will be analyzed according to 3 separate population cohorts:

ITT Population – all subjects randomized and grouped according to their randomization assignment (as randomized). The ITT will be used for the analyses of the primary and secondary effectiveness endpoints.

Per Protocol Population – ITT subjects that met the following conditions:

- Met all protocol eligibility criteria
- Had treatment consistent with randomization schedule
- Completed the 24-month medication washout without secondary surgical intervention to control IOP or additional procedures that could affect IOP (such as cyclodialysis cleft)

- Had preoperative visual field mean deviation (MD) of <0
- Without major protocol deviation established before the data review and database closure

Safety Population – all subjects who were randomized and treated. Subjects in the Hydrus group will be grouped according to whether the implantation procedure was attempted (as treated) and includes those subjects for whom implantation was not successful.

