5.0 STUDY METHODS

A. SELECTION OF PATIENTS

Only subjects who meet the inclusion and exclusion criteria will be eligible for enrollment in this study.

B. GLAUCOMA DIAGNOSIS

Glaucoma is a progressive optic neuropathy that results in characteristic optic disc and visual field changes. To qualify for the study, all subjects must have optic disc changes characteristic of glaucoma.

C. INCLUSION CRITERIA

Subjects must meet the following inclusion criteria to be eligible for the study eye:

- Male and female patients, at least 45 years of age
- An operable age-related cataract with BCVA of 20/40 or worse, eligible for phacoemulsification; if BCVA is better than 20/40, testing with a BAT meter on a medium setting must result in BCVA 20/40 or worse
- A diagnosis of POAG treated with 1 to 4 hypotensive medications
- Optic nerve appearance characteristic of glaucoma
- Medicated IOP ≤ 31 mmHg
- Diurnal IOP ≥ 22 mmHg and ≤ 34 mmHg after wash out of ocular hypotensive medications
- IOP increase > 3 mmHg after wash out of ocular hypotensive medications
- Visual field examination using Humphrey 24-2 SITA standard, meeting protocol specified minimum criteria for glaucoma defined as:
 - 1. **Mild:** visual field loss on Humphrey visual field testing, with mean deviation (MD) between 0 and -6dB; fewer than 25% of points depressed below the 5% level and fewer than 15% of points depressed below the 1% level on pattern deviation plot; and no point within central 5° with sensitivity <15dB.
 - 2. Moderate: visual field loss on Humphrey visual field testing, with mean deviation worse than -6dB but no worse than -12dB; fewer than 50% of points depressed below the 5% level, and fewer than 25% of points depressed below the 1% level on pattern deviation plot; no points within central 5° with sensitivity of ≤0dB; and only one hemifield containing a point with sensitivity <15dB within 5° of fixation.

- In subjects where the VF exam is not confirmatory for glaucomatous defect, retinal nerve fiber layer optical scanning laser imaging supporting ophthalmoscopy findings shall be performed
- Shaffer grade ≥ III in all four quadrants
- Cup:disc (c:d) ratio ≤ 0.8
- Absence of peripheral anterior synechiae (PAS), rubeosis or other angle abnormalities that could impair placement of the implant
- Subject is able and willing to attend scheduled follow-up exams for 2 years post-operatively (and up to 5 years postoperatively as part of a post-approval study)

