- Subject understands and signs the informed consent

D. Intraoperative Eligibility Criteria

Individuals who meet the following intraoperative eligibility criteria in the study eye will be randomized into the treatment or control arms of this study.

Subjects must have:

- An intact and centered capsulorrhexis
- An intact posterior capsular bag
- A well-centered monofocal IOL placed in the capsular bag
- A clear view of an open angle and visualization of the angle with direct gonioscopy following intracameral instillation of a miotic agent

Subjects must not have:

- Evidence of zonular dehiscence/rupture
- Intraoperative floppy iris syndrome

E. EXCLUSION CRITERIA

Excluded from the study will be individuals with the following characteristics. Unless specified otherwise, all ocular criteria refer to the study eye only.

- Closed angle forms of glaucoma
- Congenital or developmental glaucoma
- Secondary glaucoma (such as neovascular, uveitic, pseudoexfoliative, pigmentary, lens-induced, steroid-induced, trauma induced, or glaucoma associated with increased episcleral venous pressure).
- Use of more than 4 ocular hypotensive medications (combination medications count as two medications).
- Previous argon laser trabeculoplasty, trabeculectomy, tube shunts, or any other prior filtration or cilioablative surgery.

- Prior surgery for an ab-interno or ab-externo device implanted in or through the Schlemm's Canal.
- Inability to complete a reliable 24-2 SITA Standard Humphrey visual field on the study eye at screening (fixation losses, false positive errors and false negative errors should not be greater than 33%).
- Use of oral hypotensive medication for glaucoma for treatment of the fellow eye.
- Subjects with advanced glaucoma or any subject who presents with an unacceptable risk to the subject of a washout of ocular hypotensive medications.
- Best corrected visual acuity worse than 20/80 in the fellow eye.
- A 24-2 SITA Standard Humphrey visual field mean deviation (MD) of worse than -12dB in the fellow eye.
- Central corneal thickness > 620 microns and < 480 microns.
- Proliferative diabetic retinopathy.
- Previous surgery for retinal detachment.
- Previous corneal surgery or clinically significant corneal dystrophy, e.g.,
 Fuch's dystrophy (>12 confluent guttae)
- Unclear ocular media preventing visualization of the fundus or anterior chamber angle.
- Degenerative visual disorders such as wet age-related macular degeneration.

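### The secondary IOP-change endpoint reads as an unadjusted comparison of mean change; adjusting for the baseline washed-out IOP already collected would usually narrow its confidence interval at no data cost

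*Combined protocol and SAP*

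**What the plan says.** The secondary effectiveness endpoint is in section 7.0 B of the combined protocol and SAP: "The mean diurnal unmedicated IOP change from baseline at 24 months was compared between the Hydrus group and control group". The only further instructions are that "Each endpoint requires a comparison between the Hydrus and control groups" and, in section 7.0 C, that "The ITT will be used for the analyses of the primary and secondary effectiveness endpoints". No test, model, covariate or confidence-interval method is given for this endpoint, and baseline adjustment is not mentioned anywhere in the documents.

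The covariate is already in the data. Table 5 (section 6.0) has a row "Washed Out Diurnal IOP (Goldmann Applanation Tonometry", marked at baseline, 12 months and 24 months. Section 5.0 C makes the baseline value an entry condition: "Diurnal IOP ≥ 22 mmHg and ≤ 34 mmHg after wash out of ocular hypotensive medications". Section 5.0 D says that subjects who pass the intraoperative checks "will be randomized into the treatment or control arms of this study", but gives no allocation ratio.

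**The concern.** Subtracting baseline from the 24-month value fixes the coefficient of baseline at 1. In a trial that selects on a high washed-out pressure, the regression of the later value on baseline will often have a slope below 1. Subtraction then over-corrects and adds noise. ANCOVA estimates the slope instead of assuming it.

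What is at stake is precision, not validity. The estimate of the Hydrus effect on mean IOP may carry a wider interval than the same data support, on an endpoint for which every baseline measurement has already been paid for.

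**Working it through.** **Inputs.** The plan has no figure to reproduce: it states no SD, correlation, allocation ratio, sample size or interval width. The only anchor is the entry range of 22 to 34 mmHg. A uniform spread over it has SD 12/√12 = 3.46. Everything else is assumed:

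- baseline SD, s0: 2.0 to 3.46 mmHg
- residual SD of 24-month IOP given baseline, se: 3.5 mmHg (2.5 to 5.0 as sensitivity)
- slope of 24-month on baseline IOP: 0.3 to 0.7

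**Formulas (large samples, complete data).** Let b1 and b0 be the arm slopes, p1 and p0 the allocation shares, and b* = p1·b1 + p0·b0.

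- Change score: N·Var = [se² + s0²(b1−1)²]/p1 + [se² + s0²(b0−1)²]/p0
- ANCOVA: the same expression with b* in place of 1
- ANCOVA with centred treatment-by-baseline term: N·Var = se²/p1 + se²/p0 + s0²(b1−b0)²

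With a common slope b, the ANCOVA-to-change variance ratio is se²/[se² + s0²(1−b)²] at any allocation. It is below 1 unless b = 1. The ratio of interval widths is its square root.

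**Common slope, se = 3.5 (se² = 12.25).**

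| s0 | b | Variance ratio | Interval narrower by |
|---|---|---|---|
| 3.46 | 0.3 | 12.25/18.12 = 0.676 | 17.8% |
| 2.5 | 0.5 | 12.25/13.81 = 0.887 | 5.8% |
| 2.0 | 0.7 | 12.25/12.61 = 0.971 | 1.4% |

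The middle row is worth 1/0.887 − 1, or about 13% more subjects. Keeping s0 = 2.5 and b = 0.5 and varying se over 2.5, 3.0, 4.0 and 5.0 gives intervals 10.6%, 7.7%, 4.6% and 3.0% narrower.

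**Different slopes.** With b1 and b0 each anywhere in 0.3 to 0.7, s0 in 2.0 to 3.46, and allocation 1:1, 2:1 or 1:2, the variance ratio stays between 0.676 and 0.971.

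**Where ANCOVA can lose.** This takes unequal allocation and slopes on either side of 1. Two cases at 2:1, with the larger arm's slope first:

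- s0 = 2.5, slopes 0.5 and 1.1, so b* = 0.7. Change: 13.8125×1.5 + 12.3125×3 = 57.66. ANCOVA: 12.50×1.5 + 13.25×3 = 58.50, ratio 1.015. With interaction: 12.25×4.5 + 6.25×0.36 = 57.375, ratio 0.995.
- s0 = 3.46 (s0² = 12), slopes 0.3 and 1.2, so b* = 0.6. Change: 18.13×1.5 + 12.73×3 = 65.39. ANCOVA: 13.33×1.5 + 16.57×3 = 69.71, ratio 1.066. With interaction: 55.125 + 12×0.81 = 64.85, ratio 0.992.

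At 1:1 the same slopes give 0.981 and 0.951, so ANCOVA gains without the interaction.

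In general, N·[Var(change) − Var(interaction form)] = s0²·[(b1−1)√(p0/p1) + (b0−1)√(p1/p0)]². This cannot be negative, so in large samples the interaction form is never less precise than the change score.

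**Simulation.** Two sets of 6,000 runs used a true difference of −2 mmHg and complete data. All three estimators averaged −2.0. With 800 against 400 subjects and slopes 0.3 and 1.2, the ANCOVA ratio was 1.07, falling to 0.99 with the interaction. With baseline truncated to 22 to 34 mmHg (SD about 2.5) and a common slope of 0.5, the ratio was 0.88 to 0.90, both for 200 against 100 and for 150 against 150. This agrees with the 0.887 above.

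**The case against.** The strongest reply is that the plan never says the comparison is unadjusted. ANCOVA of change on arm and baseline is also a between-group comparison of mean change, and section 7.0 names no test or model for any endpoint. So the unadjusted reading is an inference from silence. That is true, and it is why the point is put as how the sentence reads. The request is the same either way: name the estimator, and choose the one that uses the baseline value.

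A second reply is that the gain cannot be derived from the documents and that 1% to 18% holds the residual SD at 3.5. This also stands as a limit on the figure. Crossing all the assumed inputs widens the range to 0.7% (s0 = 2.0, slope 0.7, se = 5.0) up to 28% (s0 = 3.46, slope 0.3, se = 2.5). A slope of 0.9 with s0 = 2.5 and se = 3.5 gives only 0.25%. Each of these is still a gain, but none is an estimate for this trial.

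Third, this is efficiency on a secondary endpoint, and the past tense in section 7.0 B suggests the analysis may already have been run. Both are fair. They limit the weight of the point and decide how the adjusted result should be labelled; they do not make the unadjusted analysis the better choice.

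**Conclusion.** The point holds, as an improvement rather than an error. With randomised arms and 24-month unmedicated values complete or ignorably missing, the unadjusted comparison of change is unbiased. With a common slope, or with 1:1 allocation, it is in large samples no more precise than ANCOVA on baseline; with a common slope it is strictly less precise unless the slope is 1. Under the main assumptions the interval would be 1% to 18% narrower, with 6% as a middle case. The exception, unequal allocation with slopes straddling 1, is small in the cases tried and is removed by a centred interaction term. It matters only because no allocation ratio is given.

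Baseline adjustment does not settle how unobserved or unusable 24-month values are handled. Section 7.0 A counts subjects as non-responders if "they were missing 24-month IOP assessment outcomes, if ocular hypotensive medications were not washed out at the 24-month visit", or after IOP-affecting surgery, but that rule serves only the binary primary endpoint. If such events differ by arm, either estimator can be biased.

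**What to change.** State in section 7.0 B that the 24-month treatment difference will be estimated by ANCOVA of washed-out diurnal IOP (or its change, which gives the same treatment difference) on arm and baseline washed-out diurnal IOP, plus any factors used to stratify randomisation, and reported with a 95% confidence interval. If allocation is unequal, add a treatment-by-baseline term with baseline centred at its overall mean, and use a standard error that allows for that mean being estimated.

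If the unadjusted analysis has already been run, keep it as the reported result and add the adjusted one as supplementary, labelled post hoc.

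No new data are needed. The cost is one or two lines of SAP text before analysis, or one supplementary analysis after it. As a separate matter, state how missing, non-washed-out and post-surgery 24-month values enter this continuous endpoint.

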- Clinically significant ocular pathology, other than cataract and glaucoma.
- Clinically significant ocular inflammation or infection within 6 months prior to screening.
- Presence of extensive iris processes that obscure visualization of the trabecular meshwork.
- Unable to discontinue use of blood thinners in accordance with surgeon's standard postoperative instructions.
- Known or suspected elevated episcleral venous pressure due to Sturge Weber, nanophthalmos, orbital congestive disease.
- Uncontrolled systemic disease that in the opinion of the Investigator would put the subject's health at risk and/or prevent the subject from completing all study visits.
- Current participation or participation in another investigational drug or device clinical trial (which includes the fellow eye) within the past 30 calendar days.
- Pregnant or nursing women; or women of child bearing age not using medically acceptable contraceptives.

F. CONSENT

Participation in the study is voluntary. When it has been established that the subject is eligible for possible enrollment into the study, written informed consent (ICF) will be obtained.

G. ENROLLMENT

Patients who sign the informed consent form (ICF) are considered enrolled. Only after ICF is obtained should study specific exams and wash out be initiated.

H. WASH OUT

After the subject has successfully completed the preoperative screening exam, the subject will be instructed to discontinue ocular hypotensive medications in the designated treatment eye for the appropriate washout period.

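### Adverse events from the pre-operative washout appear in no planned summary when the subject is never randomized

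*Combined protocol and SAP*

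**What the plan says.** Section 5.0 G sets the point of entry: "Patients who sign the informed consent form (ICF) are considered enrolled". It continues "Only after ICF is obtained should study specific exams and wash out be initiated", so the pre-operative washout is a procedure that the study imposes on people already counted as enrolled. Randomization comes later, during surgery. Section 5.0 D states: "Individuals who meet the following intraoperative eligibility criteria in the study eye will be randomized".

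Between these two points, Table 5 in Section 6.0 marks an AE assessment at the Baseline visit, with a footnote that restricts its scope: "Only adverse events associated with the ocular medication wash out".

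The reporting rule is in Section 7.0 B: "anticipated and unanticipated AEs will be reported for all subjects randomized in the study". Section 7.0 C adds "Subjects will be analyzed according to 3 separate population cohorts". These are the ITT set (everyone randomized), the Per Protocol set (a subset of ITT) and the Safety set, defined as "all subjects who were randomized and treated".

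**The concern.** Data collection starts before randomization, but planned reporting starts at randomization. Between the two is a group who consented, stopped their medication because the study asked them to, and were then not randomized. They bore the washout risk, and the plan has no place to show what happened to them.

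What is at stake is the absolute description of a risk created by the trial design. If washout AEs are summarised only in those who reached randomization, the result describes people who got through washout and met the entry limits on IOP. A sponsor, ethics committee or later trial that uses it to judge the hazard of washout would be reading a selected group. The treatment effect and the device-versus-control safety contrast are not at stake.

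**Working it through.** The plan states no washout AE rate or screen-failure rate, so there is no figure to reproduce. The check is to follow a subject through the study and see where an AE would be collected and where it would be reported.

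| Stage | Section | AE collected? | In a planned summary? |
|---|---|---|---|
| Consent (enrolled) | 5.0 G | Not scheduled | No |
| Washout under way, stops before Baseline | 5.0 H, Table 5 | Not scheduled | No, as never randomized |
| Baseline visit, washed out | Table 5 footnote | Yes, washout-associated only | Only if later randomized |
| Surgery, randomized | 5.0 D, 7.0 B | Yes | Yes |
| 12- and 24-month washouts | Table 5, 7.0 B | Yes | Yes, as already randomized |

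**Do other sections close the gap?**

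- Section 7.0 C: no. The Safety set is no wider than the randomized set, and Per Protocol lies within ITT.
- Section 8.E: no. It directs AE evaluation at people exposed to study treatment. That does not plainly include someone who has only been washed out, and it fits poorly with the Baseline footnote.
- Section 8.K: in part. Serious AEs and unanticipated device effects go to the sponsor within 10 working days, with no wording that confines this to randomized subjects. This is notification, not a planned summary, and it leaves out non-serious events.

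**Is non-randomization related to washout harm?** Section 5.0 C requires a washed-out diurnal IOP of 22 to 34 mmHg and a rise of more than 3 mmHg. The upper limit removes eyes with the highest pressures off medication. The lower limit and the minimum rise remove eyes that changed little or stayed low. The intraoperative criteria remove subjects for reasons such as capsule or zonule damage, floppy iris or a poor angle view, which do not imply a washout AE. Selection therefore works in more than one direction.

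**Size, in symbols.** Let f be the share of washout starters never randomized, a_N their washout AE rate, and a_R the rate in those randomized.

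- Rate among all starters: A = (1 − f) × a_R + f × a_N
- Rate visible in randomized subjects: a_R
- Gap: A − a_R = f × (a_N − a_R)

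The documents give none of f, a_N or a_R. The values below are assumptions that show only how the gap behaves, with a_R = 1% throughout:

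| f | a_N | A | Gap (percentage points) |
|---|---|---|---|
| 20% | 3% | 0.8 × 1% + 0.2 × 3% = 1.4% | +0.4 |
| 50% | 5% | 0.5 × 1% + 0.5 × 5% = 3.0% | +2.0 |
| 20% or 50% | 1% | 1.0% | 0 |
| 20% | 0% | 0.8 × 1% = 0.8% | −0.2 |
| 50% | 0% | 0.5 × 1% = 0.5% | −0.5 |

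The sign depends wholly on whether a_N exceeds a_R. The upper IOP limit makes that plausible, but the documents do not settle it.

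**The case against.** The strongest reply is that Section 7.0 B sits among the endpoints and describes the comparative safety results. It says whose AEs enter those results and does not forbid listing earlier events. That is fair: exclusivity is inferred. The inference still matters, because no other section adds a wider reporting set, and an analyst following the plan would produce no such table.

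A second reply is that the worst harms are not lost. Under Sections 8.B and 8.C, a sight-threatening event can qualify as serious on the investigator's judgement, and Section 8.K brings it to the sponsor. This also stands. A reader might infer that washout harm is discarded altogether, and the documents do not support that. What is missing is a planned summary with a denominator.

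A third reply concerns the mechanism. A reader might infer that an eye above 34 mmHg after washout is itself an unreported AE, or that the subjects left out are precisely the harmed ones. Neither follows. Exceeding 34 mmHg is an entry failure that no section defines as an AE, and a rise in pressure is the expected effect of washout and is required for entry. The IOP-elevation event listed in Section 8.L is a rise of at least 10 mmHg over baseline, more than 1 month after surgery. Many subjects also go unrandomized for reasons unrelated to harm.

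Finally, a randomized-and-treated set suits the device-safety question. That is correct, and the fix keeps it.

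**Conclusion.** The gap is real and limited. Under the plan as written, pre-operative washout AEs in subjects never randomized enter no planned summary, and what is reported on that washout is conditional on reaching randomization. This conclusion rests on the sequence of consent, washout, Baseline and intraoperative randomization, and on the absence of any wider reporting set. It needs no assumed rate.

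Understatement of the washout risk is plausible, not demonstrated. A reader might take the illustrative 1.4% to 3.0% against 1.0% as an estimate. It is not one: all inputs are assumed, equal rates give a gap of zero, lower rates in the non-randomized reverse it, and no section commits the sponsor to reporting a washout AE rate at all.

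The omission precedes randomization, so it does not bias the Hydrus-control comparison, and no endpoint or test changes. It is a worthwhile improvement to harm reporting, not a threat to the trial's main conclusions.

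**What to change.** 1. In Section 7.0, state that washout-associated AEs and serious AEs will be summarised descriptively for all enrolled subjects who began the pre-operative washout, with that number as the denominator, split into randomized and not randomized with the reason for non-randomization.
2. Keep the randomized set and the Safety set for the between-arm safety comparison.
3. Reconcile Section 8.E with the Table 5 Baseline footnote, so that AE evaluation explicitly includes washout-only subjects and captures those who stop before the Baseline visit. Table 5 schedules no AE assessment for them at present, so existing data collection would not fill the whole table.

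The cost is one short statement and one extra table, a small amount of additional AE recording for subjects who stop before Baseline, and a washout AE rate that may look less favourable. No endpoint, between-arm analysis or clinical rule is altered.
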